12.7 Interim analyses

For the purpose of earlier dissemination of results, an interim analysis will be performed after all enrolled participants have either meet the criteria of at least 6 months treatment or discontinued treatment prematurely. For this analysis, only primary variables, demographics, baseline characteristics, adverse events and serious adverse events will be summarized.

Since there will be no hypothesis testing involved, statistical adjustment for the interim analysis will not be made at the stage of final analyses of efficacy and safety.

12.8 Sample size calculation

12.8.1 Primary endpoint(s)

Sample size calculations were based on the proportion of participants with no change or a reduction from Baseline (assessed at Screening Visit) in the number of gadolinium-enhancing (GdE) MRI lesions 12 months after initiating ofatumumab therapy. Three precision estimates were considered for this study:

The sample size of 100 participants is selected based on budget and early availability of interim analysis results. This sample size of 100 participants will provide us with an 8.5% precision

(half-width of 95% confidence interval), a 7.8% precision, or a 7.0% precision corresponding to estimated proportions of 75%, 80%, and 85% of participants achieving the primary endpoint.

13 Ethical considerations and administrative procedures

13.1 Regulatory and ethical compliance

This clinical study was designed and shall be implemented, executed and reported in accordance with the International Conference on Harmonisation (ICH) Harmonized Tripartite Guidelines for Good Clinical Practice, with applicable local regulations (including European Directive 2001/20/EC, US CFR 21), and with the ethical principles laid down in the Declaration of Helsinki.

13.2 Responsibilities of the Investigator and IRB/IEC

Before initiating a trial, the Investigator/institution must obtain approval/favorable opinion from the Institutional Review Board/Independent Ethics Committee (IRB/IEC) for the trial protocol, written informed consent form, consent form updates, participant recruitment procedures (e.g. advertisements) and any other written information to be provided to participants. Prior to study start, the Investigator is required to sign a protocol signature page confirming his/her agreement to conduct the study in accordance with these documents and all of the instructions and procedures found in this protocol and to give access to all relevant data and records to Novartis monitors, auditors, Novartis Quality Assurance representatives, designated agents of Novartis, IRBs/IECs, and regulatory authorities as required. If an inspection of the clinical site is requested by a regulatory authority, the Investigator must inform Novartis immediately that this request has been made.

13.3 Publication of study protocol and results

[figure not shown]
The protocol will be registered in a publicly accessible database such as clinicaltrials.gov and as required in EudraCT. In addition, after study completion (*defined as last patient last visit*) and finalization of the study report the results of this trial will be submitted for publication and posted in a publicly accessible database of clinical trial results, such as the Novartis clinical trial results website and all required Health Authority websites (e.g. Clinicaltrials.gov, EudraCT etc.).

For details on the Novartis publication policy including authorship criteria, please refer to the Novartis publication policy training materials that were provided to you at the trial Investigator meetings.

13.4 Quality Control and Quality Assurance

Novartis maintains a robust Quality Management System (QMS) that includes all activities involved in quality assurance and quality control, to ensure compliance with written Standard Operating Procedures as well as applicable global/local GCP regulations and ICH Guidelines.

Audits of Investigator sites, vendors, and Novartis systems are performed by auditors, independent from those involved in conducting, monitoring or performing quality control of the clinical trial. The clinical audit process uses a knowledge/risk based approach.

Audits are conducted to assess GCP compliance with global and local regulatory requirements, protocols and internal SOPs, and are performed according to written Novartis processes

14 Protocol adherence

This protocol defines the study objectives, the study procedures and the data to be collected on study participants. Additional assessments required to ensure safety of participants should be administered as deemed necessary on a case by case basis. Under no circumstances including incidental collection is an Investigator allowed to collect additional data or conduct any additional procedures for any purpose involving any investigational drugs under the protocol, other than the purpose of the study. If despite this interdiction prohibition, data, information, observation would be incidentally collected, the Investigator shall immediately disclose it to Novartis and not use it for any purpose other than the study, except for the appropriate monitoring on study participants.

[figure not shown]
Investigators ascertain they will apply due diligence to avoid protocol deviations. If an Investigator feels a protocol deviation would improve the conduct of the study this must be considered a protocol amendment, and unless such an amendment is agreed upon by Novartis and approved by the IRB/IEC and Health Authorities, where required, it cannot be implemented.

16.1 Appendix 1: Liver event and Laboratory trigger Definitions and Follow-up Requirements

[figure not shown]
Table 16-1 Liver event and laboratory trigger definitions

	Definition/ threshold
LIVER LABORATORY TRIGGERS	
 • 3 x ULN < ALT / AST ≤ 5 x ULN • 1.5 x ULN < TBL ≤ 2 x ULN
LIVER EVENTS	
 • ALT or AST > 5 × ULN • ALP > 2 × ULN (in the absence of known bone pathology) • TBL > 2 × ULN (in the absence of known Gilbert syndrome) • ALT or AST > 3 × ULN and INR > 1.5 • Potential Hy's Law cases (defined as ALT or AST > 3 × ULN and TBL > 2 × ULN [mainly conjugated fraction] without notable increase in ALP to > 2 × ULN) • Any clinical event of jaundice (or equivalent term) • ALT or AST > 3 × ULN accompanied by (general) malaise, fatigue, abdominal pain, nausea, or vomiting, or rash with eosinophilia • Any adverse event potentially indicative of a liver toxicity*

*These events cover the following: Hepatic failure, fibrosis and cirrhosis, and other liver damage-related conditions; the non-infectious hepatitis; the benign, malignant and unspecified liver neoplasms TBL: total bilirubin; ULN: upper limit of normal.

[figure not shown]
Table 16-2 Follow up requirements for liver events and laboratory triggers

Criteria	Actions required	Follow-up monitoring
Potential Hy's Law case ^a	
 • Discontinue the study drug immediately • Hospitalize, if clinically appropriate • Establish causality • Record the AE and contributing factors (e.g. conmeds, med hx, lab) in the appropriate CRF 	ALT, AST, TBL, Alb, PT/INR, ALP and y-GT until resolution ^c (frequency at Investigator discretion)

Criteria	Actions required	Follow-up monitoring
ALT or AST		
> 8 × ULN	
 Discontinue the study drug immediately Hospitalize if clinically appropriate Establish causality Record the AE and contributing factors (e.g. conmeds, med hx, lab) in the appropriate CRF 	ALT, AST, TBL, Alb, PT/INR, ALP and y-GT until resolution ^c (frequency at Investigator discretion)
> 3 × ULN and INR > 1.5	
 Discontinue the study drug immediately Hospitalize, if clinically appropriate Establish causality Record the AE and contributing factors (e.g. conmeds, med hx, lab) in the appropriate CRF 	ALT, AST, TBL, Alb, PT/INR, ALP and y-GT until resolution ^c (frequency at Investigator discretion)
> 5 to ≤ 8 × ULN	
 Repeat LFT within 48 hours If elevation persists, continue follow-up monitoring If elevation persists for more than 2 weeks, discontinue the study drug Establish causality Record the AE and contributing factors (e.g. conmeds, med hx, lab) in the appropriate CRF 	ALT, AST, TBL, Alb, PT/INR, ALP and y-GT until resolution ^c (frequency at Investigator discretion)
> 3 × ULN accompanied by symptoms ^b	
 Discontinue the study drug immediately Hospitalize if clinically appropriate Establish causality Record the AE and contributing factors (e.g. conmeds, med hx, lab) in the appropriate CRF 	ALT, AST, TBL, Alb, PT/INR, ALP and y-GT until resolution ^c (frequency at Investigator discretion)
> 3 to ≤ 5 × ULN (participant is asymptomatic)	
 Repeat LFT within the next week 	Investigator discretion Monitor LFT within 1 to 4 weeks

[figure not shown]
Criteria	Actions required	Follow-up monitoring
ALP (isolated)	
 If elevation is confirmed, initiate close observation of the participant 	Investigator discretion
> 2 × ULN (in the absence of known bone pathology)	
 Repeat LFT within 48 hours If elevation persists, establish causality Record the AE and contributing factors (e.g. conmeds, med hx, lab) in the appropriate CRF 	Monitor LFT within 1 to 4 weeks or at next visit
TBL (isolated)	
 Repeat LFT within 48 hours If elevation persists, discontinue the study drug immediately Hospitalize if clinically appropriate Establish causality Record the AE and contributing factors (e.g. conmeds, med hx, lab) in the appropriate CRF 	ALT, AST, TBL, Alb, PT/INR, ALP and γ -GT until resolution ^c (frequency at Investigator discretion) Test for hemolysis (e.g. reticulocytes, haptoglobin, unconjugated [indirect] bilirubin)
> 1.5 to ≤ 2 × ULN (participant is asymptomatic)	
 Repeat LFT within the next week If elevation is confirmed, initiate close observation of the participant 	Investigator discretion Monitor LFT within 1 to 4 weeks or at next visit
Jaundice	
 Discontinue the study drug immediately Hospitalize the participant Establish causality Record the AE and contributing factors (e.g. conmeds, med hx, lab) in the appropriate CRF 	ALT, AST, TBL, Alb, PT/INR, ALP and γ -GT until resolution ^c (frequency at Investigator discretion)
Any AE potentially indicative of a liver toxicity*	
 Consider study drug interruption or discontinuation Hospitalization if clinically appropriate Establish causality 	Investigator discretion

Criteria	Actions required	Follow-up monitoring
	
Record the AE and contributing factors (e.g. conmeds, med hx, lab) in the appropriate CRF	

^aElevated ALT/AST > 3 × ULN and TBL > 2 × ULN but without notable increase in ALP to > 2 × ULN ^b(General) malaise, fatigue, abdominal pain, nausea, or vomiting, or rash with eosinophilia ^cResolution is defined as an outcome of one of the following: (1) return to baseline values, (2) stable values at three subsequent monitoring visits at least 2 weeks apart, (3) remain at elevated level after a maximum of 6 months, (4) liver transplantation, and (5) death.

Based on Investigator's discretion investigation(s) for contributing factors for the liver event can include: Serology tests, imaging and pathology assessments, hepatologist's consultancy; obtaining more detailed history of symptoms and prior or concurrent diseases, history of concomitant drug use, exclusion of underlying liver disease.

16.2 Appendix 2: Specific Renal Alert Criteria and Actions and Event Follow-up

Table 16-3 Specific Renal Alert Criteria and Actions

Serum Event	Actions
Serum creatinine increase 25-49% compared to baseline	Confirm 25% increase after 24-48h Follow up within 2-5 days
Acute Kidney Injury: Serum creatinine increase \geq 50 % compared to baseline	Follow up within 24-48h if possible Consider study treatment interruption Consider participant hospitalization and specialized treatment
Urine Event	
New dipstick proteinuria \geq 1+ Albumin- or Protein-creatinine ratio increase \geq 2-fold Albumin-creatinine ratio (ACR) \geq 30 mg/g or \geq 3 mg/mmol;	Confirm value after 24-48h Perform urine microscopy Consider study treatment interruption/discontinuation
Protein-creatinine ratio (PCR) \geq 150 mg/g or $>$ 15 mg/mmol	
New dipstick glycosuria \geq 1+ not due to diabetes	Blood glucose (fasting) Perform serum creatinine, ACR
New dipstick hematuria \geq 1+ not due to trauma or menstruation	Urine sediment microscopy Perform serum creatinine, ACR

Additional specialized assessments are available to assess renal function or renal pathology. *(Note: In exceptional cases, when a nephrologist considers a renal biopsy, it is recommended to make slide specimen available for evaluation by the RSG to potentially identify project-wide patterns of nephrotoxicity.)*

Whenever a renal event is identified, a detailed participant history and examination are indicated to identify and potentially eliminate risk factors that may have initiated or contributed to the event:

- Blood pressure assessment (after 5-minute rest, with an appropriate cuff size)
- Signs and symptoms like fever, headache, shortness of breath, back or abdominal pain, dysuria or hematuria, dependent or periorbital edema
- Changes in blood pressure, body weight, fluid intake, voiding pattern or urine output
- Concomitant events or procedures such as trauma, surgical procedures, cardiac or hepatic failure, contrast media or other known nephrotoxin administration, or other diseases or causes, e.g. dehydration due to delirium, tumor lysis

Table 16-4 Renal Event Follow up

Follow-up of Renal Events

Assess, Document & Record in eCRF

- Urine dipstick and sediment microscopy evidence of DIN: crystals, red blood cells (dysmorphic/glomerular vs. non dysmorphic/non-glomerular), white blood cells, tubular epithelial cells
- Blood pressure and body weight
- Serum creatinine, BUN, electrolytes (sodium, potassium, phosphate, calcium), bicarbonate and uric acid
- Urine output

Review and record possible contributing factors to the renal event (co-medications, other co-morbid conditions) and additional diagnostic procedures (MRI etc.) in the eCRF

Monitor participant regularly (frequency at the Investigator's discretion) until:

- Event resolution: (sCR within 10% of baseline or PCT < 1 g/g Cr, or ACR <300mg/g Cr)
- or
- Event stabilization: sCR within +/- 10% variability over last 6 months or PCR stabilization at a new level with +/- 50% variability over last 6 months
 - Analysis of urine markers collected over the course of the DIN event
-

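### Renal follow-up (Protocol Table 16-4): the urine resolution limit lies above the alert limit and the terms are joined by *or*, so some confirmed renal alerts already meet the rule for ending monitoring

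*Protocol*

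**What the plan says.** Table 16-3 in Protocol section 16.2 lists the renal alerts. For urine they include "Albumin-creatinine ratio (ACR) \geq 30 mg/g", "Protein-creatinine ratio (PCR) \geq 150 mg/g" and "Albumin- or Protein-creatinine ratio increase \geq 2-fold", plus new dipstick findings of 1+ or more. Its proteinuria row asks for confirmation after 24-48 hours, urine microscopy, and consideration of interrupting or stopping study drug. For serum the first tier is "Serum creatinine increase 25-49% compared to baseline", and the second is a rise of 50% or more, labelled acute kidney injury.

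Section 10.2.2 directs every trigger or event in Table 16-3 to the follow-up in Table 16-4. That table first sets out a work-up (dipstick and sediment, blood pressure and weight, creatinine and other chemistry, urine output, contributing factors). It then says "Monitor participant regularly", at a frequency the investigator chooses, until one of two end points is met. The first is "Event resolution: (sCR within 10% of baseline or PCT < 1 g/g Cr, or ACR <300mg/g Cr". The second, joined to it by *or*, is "Event stabilization: sCR within +/- 10% variability over last 6 months or PCR stabilization at a new level", with a 50% variability band for PCR over the last 6 months.

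PCT is not defined. The abbreviation list and the stabilization bullet use PCR.

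**The concern.** A resolution rule should be met only when the finding that opened the event has gone away. Here the urine closing limit lies above the urine opening limit, so the sample that confirms an alert can also end the obligation to monitor it. The *or* adds a second fault: a normal result on one analyte can close an event raised by another.

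At stake is safety follow-up. A site that applies Table 16-4 literally could stop regular monitoring of confirmed proteinuria for which Table 16-3 has just asked it to consider stopping study drug. The same site could also treat a creatinine rise in the acute kidney injury range as resolved because the urine albumin is not high.

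**Working it through.** The plan gives no derived figure to reproduce here, so the check compares limits and tests the logic.

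**Inputs.** Alert limits (Table 16-3): ACR 30 mg/g, PCR 150 mg/g, serum creatinine (sCR) rise 25%. Resolution limits (Table 16-4): ACR 300 mg/g, PCT 1 g/g = 1000 mg/g, sCR within 10% of baseline. Reading PCT as PCR is an assumption; the ACR result does not need it.

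**Step 1: closing limit divided by opening limit.**
- ACR: 300/30 = 10. Overlap 30 to below 300 mg/g.
- PCR, if PCT means PCR: 1000/150 = 6.7. Overlap 150 to below 1000 mg/g.
- sCR, taken alone: 10/25 = 0.4. No overlap.

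**Step 2: does the overlap depend on how the rule is read?**
- *Or*, as written: ACR 30, 150 and 299 mg/g are each an alert and each resolved.
- Only the analyte that raised the alert: ACR 30 to 299 mg/g still meets both limits.
- *And*: with sCR unchanged, PCR 500 mg/g and ACR 150 mg/g, the alert is open and all three closing terms are met. Under this reading the overlap needs stable creatinine and PCR below 1 g/g.

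**Step 3: closure across analytes under the written *or*.**

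| sCR change | PCR (mg/g) | ACR (mg/g) | Alert? | Resolved? | Closed by |
|---|---|---|---|---|---|
| +60% | 100 | 10 | yes | yes | urine terms |
| 0% | 1500 | 500 | yes | yes | sCR term |
| +15% | 1200 | 150 | yes | yes | ACR term alone |
| +60% | 1500 | 500 | yes | no | - |
| +15% | 1200 | 350 | yes | no | - |

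The first row is a creatinine rise above 50% that counts as resolved. The second is heavy proteinuria that counts as resolved because creatinine has not moved.

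**Step 4: how long until the next scheduled urine test?** Protocol Table 8-1 schedules post-baseline dipsticks at Months 1, 6 and 12. SAP Table 2-3 puts these at days 31, 184 and 366. The gaps are 184 - 31 = 153 days and 366 - 184 = 182 days. With windows of 3 days either side they are 147-159 and 176-188 days.

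**Step 5: does lowering the limit suffice?** Not for the 2-fold trigger. A rise in ACR from 10 to 20 mg/g is an alert (20/10 = 2), yet 20 is below 30 and would close at once. Requiring the ratio also to be below twice the reference value prevents this, since 20 is not below 2 x 10. On whole-number values with the reference ratio below the alert limit, a closing limit of ACR <30 alone leaves 210 alert pairs that close on the same sample, and PCR <150 alone leaves 5550. With the added condition both counts are 0. These are logic checks, not incidences.

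**The case against.** The strongest defence is that the limits are graded on purpose: a sensitive alert, then a higher limit for continued monitoring. There is a parallel in Appendix 1, where asymptomatic ALT or AST above 3 and up to 5 x ULN gets a repeat test and then largely investigator discretion. A participant with stable, pre-existing ACR of 40 mg/g might never fall below 30, which would be a practical reason for a higher closing limit. This is plausible, but nowhere does the protocol state it, and Table 16-4 calls the limit resolution. It also would not explain closure of a creatinine event by a urine value. The pre-existing case does stand as a constraint on the fix.

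The second defence is that other rules cover the gap, and most of it stands. Confirmation, the Table 16-3 actions and the Table 16-4 work-up do not depend on the resolution limit. Section 8.4.5 requires abnormal results to be assessed against the adverse event criteria, and laboratory adverse events to be repeated until normal or no longer clinically significant. Section 10.1.1 requires an adverse event to be followed until it resolves or is judged permanent. Section 10.2.2 also narrows the proteinuria trigger to a dipstick finding confirmed by a doubling of ACR or PCR, and neither ratio is on the routine panel in Table 8-5.

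A reader might go further and infer that only the urine rule overlaps its alert, and that a liver trigger sample can never close its own event. The documents do not support either inference. The serum limits are free of overlap only when read for creatinine alone; under the written *or* they are not (Step 3). Liver resolution includes "1) return to baseline values, (2) stable values at three subsequent monitoring visits at least 2 weeks apart". Exclusion 17 admits total bilirubin up to 3 x ULN, and bilirubin above 2 x ULN is a liver event. A participant without Gilbert syndrome whose baseline and on-study values are both 2.5 x ULN meets the event and resolution definitions on one sample.

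**Conclusion.** Wrong as written, and minor. Confirmed urine alerts with ACR 30-299 mg/g already satisfy the rule for ending regular monitoring, whether the rule is read literally or for the triggering analyte only. The extension to PCR 150-999 mg/g rests on PCT meaning PCR. The closures across analytes rest on reading *or* as it is printed.

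It would be tempting to conclude that Table 16-4 leaves proteinuria unmonitored once confirmed. That goes too far. The work-up and the adverse event rules remain, and so do scheduled dipsticks and chemistry. What is left is mainly asymptomatic proteinuria that the investigator does not class as an adverse event, in the intervals of about 153 and 182 days between scheduled urine tests. The documents give no distribution of ACR or PCR, so the number of participants affected cannot be stated. No endpoint or planned analysis is touched; SAP Table 5-1 lists neither ratio.

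**What to change.** Reword the end points in Table 16-4 so that resolution is judged on the analyte that raised the alert:

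- Serum events: sCR within 10% of baseline.
- Urine events: ACR <30 mg/g or PCR <150 mg/g as applicable and, where the trigger was a rise of 2-fold or more, the ratio also below twice the reference value; or return to a documented pre-treatment value.
- Stabilization: keep the 6-month alternative and extend it to ACR. It now names only sCR and PCR, so persistent ACR just above 30 mg/g would have no exit of its own.
- Correct PCT to PCR.

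The pre-treatment clause lets a stable, pre-existing elevation close at once. That is deliberate. Dipstick glycosuria and hematuria are alerts in Table 16-3 with no closing term of their own, so analyte matching needs a line for them too.

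The cost is wording in one appendix table, plus some extra ACR or PCR repeats outside the routine panel. In participants with persistent low-grade proteinuria these could run for up to about 6 months. No baseline ratio is scheduled, so the 2-fold and pre-treatment clauses work only where an earlier ratio exists. The SAP's latest amendment is already near database lock, so the benefit lies in any remaining follow-up and in reuse of this appendix.

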16.3 Appendix 3: Safety Monitoring Guidance

16.3.1 Guidance on monitoring of Participants with symptoms of neurological deterioration suggestive of PML

Should a participant develop any unexpected neurological or psychiatric symptom/signs in the opinion of Investigator (e.g. cognitive deficit, behavioral changes, cortical visual disturbances or any other neurological cortical symptoms/signs any symptom/sign suggestive of an increase of intracranial pressure) or accelerated neurological deterioration, the Investigator should schedule a complete physical and neurological examination and an MRI as soon as possible before beginning any steroid treatment. Conventional MRI as defined in the protocol as well as additional scanning such as FLAIR and Diffusion-weighted imaging (DWI) sequences are recommended to aid in differential diagnosis. The local neuro-radiologist must evaluate the MRI. The Investigator will contact the Medical Advisor at Novartis and a clinical trial team (CTT) member to discuss findings and diagnostic possibilities as soon as possible. A copy of the unscheduled MRI should be sent to the MRI Evaluation Center designated by Novartis as soon as possible. AE/SAEs need to be filed as appropriate.

If the MRI shows new MS lesions consistent with an MS relapse, assessment and treatment of the relapse will be performed as described in the protocol ([Section 6.2.3](#) and [Section 8.3.1](#)). In case of new findings in the MRI images in comparison with the previous available MRI, which are not compatible with MS lesions, the study drug will be discontinued and other diagnostic evaluations need to be performed at the discretion of the Investigator. If new lesions are detected on the MRI, which may be infectious in origin, it is recommended to collect a cerebrospinal fluid sample if indicated. Analysis of the Cerebrospinal Fluid (CSF) sample including cellular, biochemical, Polymerase Chain Reaction, and microbiological analysis (e.g. herpes virus, JC virus) to confirm/exclude an infection should be performed. In the event of suspected CNS

infection (PML), a CSF aliquot should be sent to a central laboratory (designated by Novartis) for confirmatory testing.

Only after the evaluations have excluded diagnoses other than MS and after discussion with the Medical Advisor at Novartis and a CTT member, the study drug may be restarted.

